- Mark out the loose skin to be treated into two separate, large zones using a surgical marking pen. Move the internal subdermal electrode and external electrode smoothly back and forth within each large zone until the desired temperature has been reached, and then continue to treat that zone at the desired temperature for 5 minutes.
- After the Sound Indicator emits the audible indicator that the desired temperature is reached, continue heating your treatment zone for 5 minutes to optimize subdermal stimulation. Once heated for 5 minutes at the desired temperature, move to the next large thermal grid until all

I N M O D E

aesthetic solutions

Clinical Evaluation of Safety and Efficacy of Radio-Frequency Assisted Lipolysis (RFAL) of Breast Envelope and Nipple-Areolar Complex (NAC) Position

*Protocol No:
DO607738A*

Rev. Date: August, 2018

SIRB ID: 6254

grids have been treated and the subdermal skin has had the temperature elevated to the desired end temperature.

- When desired amount of energy is delivered switch device to the Standby mode and remove internal electrode from the body.
- Introduce a small to medium suction with connected syringe or mechanical aspiration system through the same incision to the treated layer of fat.
- It is recommended that a gentle aspiration be performed by employing blunt, bullet tipped, vented cannulas and turning the wall aspiration pressure down.
- Apply vacuum to the syringe or aspiration system to remove the excessive fluids from the body.
- Assess the desired contour endpoint by visual inspection of the nipple areola complex.
- Close incisions with sutures. If your customary practice is to leave your liposuction access ports non-sutured, you may do so.
- Following the procedure, use standard post operation pressure dressing including lipoplasty compression garments. If the skin laxity on the breasts is significant, consideration for a closed drainage system may be made.

VISIT 3:

FOLLOW UP

Follow-up session 1-week post treatment. Photographs will be taken. Any adverse events and their persistence will be recorded. [Patient and physician satisfaction forms to be completed on 5-point scale at each post op visit]

I N M O D E
aesthetic solutions

Clinical Evaluation of Safety and Efficacy of Radio-Frequency Assisted Lipolysis (RFAL) of Breast Envelope and Nipple-Areolar Complex (NAC) Position

Protocol No:
DO607738A

Rev. Date: August, 2018

SIRB ID: 6254

VISIT 4:

FOLLOW UP

Follow-up session 6-weeks post treatment. Photographs will be taken. Any adverse events and their persistence will be recorded. Patient and PI will fill in the questionnaires.

VISIT 5:

FOLLOW UP

Follow-up session 3 months post treatment. Photographs will be taken. Any adverse events and their persistence will be recorded. Patient and PI will fill in the questionnaires.

VISIT 6:

FOLLOW UP

Follow-up session 6 months post treatment. Photographs will be taken. Any adverse events and their persistence will be recorded. Patient will undergo mammogram and results will be recorded in CRF. Patient and PI will fill in the questionnaires.

VISIT 7 (If Applicable):

FOLLOW UP

Follow-up session 12 months post treatment. Photographs will be taken. Any adverse events and their persistence will be recorded. Patient and PI will fill in the questionnaires.

TREATMENT PARAMETERS STUDY

The investigator may decide to have different parameters on the same patient. For example, the right side may be treated in lower power for longer time, and on the left side higher power for shorter duration. The total energy (kJ) deposited into the tissue may vary.

I N M O D E
aesthetic solutions

Clinical Evaluation of Safety and Efficacy of Radio-Frequency Assisted Lipolysis (RFAL) of Breast Envelope and Nipple-Areolar Complex (NAC) Position

Protocol No:
DO607738A

Rev. Date: August, 2018

SIRB ID: 6254

POST-TREATMENT CARE

- The incision's area should be covered with medical dressing and with firm pressure dressing or compression garment if required. Compression may be needed per the physician's order. The subject should be instructed that there may be drainage from incision area and that it should be consistently cleaned and disinfected.
- In case of side effects; burns, blistered or ulcerated skin can be treated with a prescribed antibiotic ointment, burn treatment cream or other prescribed medication.
- Bed rest may be helpful after the treatment.
- Discomfort, if any, may be relieved by placing a cool (not frozen) pack on treated area.
- During the first 1-2 weeks following treatment, care should be taken to prevent trauma to the treated site: avoid hot baths, excessive physical activities, etc.
- A prophylactic antibiotic regimen may be prescribed for subjects starting one day before treatment until one-week post-treatment according to physician discretion. Prophylactic antibiotics should be administered on the day of treatment and continued for a minimum of 2 doses following the RAL procedure.
- Discomfort can be reduced by cool compresses or standard post-operative analgesic.
- Compression garments may be used for up to 6 weeks.
- Appropriate vigorous exercise restrictions should be instituted.
- Subject is to contact physician if there is any indication of infection, fever, excessive swelling, redness, undue pain, shortness of breath, swelling of the ankles, chest pain, irregular heart beat or any other unusual or untoward symptom.

I N M O D E
aesthetic solutions

Clinical Evaluation of Safety and Efficacy of Radio-Frequency Assisted Lipolysis (RFAL) of Breast Envelope and Nipple-Areolar Complex (NAC) Position

Protocol No:
DO607738A

Rev. Date: August, 2018

SIRB ID: 6254

SAFETY AND RESULT MEASUREMENTS

Photography

At each of the specified time points (before the treatment and at the follow-up visits), photos of the body should be taken, including a frontal photo, back photo and two side images of the body from knee up to breast line as it is shown in the picture on the next page. Hands of the subject should be at the side of the body in the position that does not block and does not shade the treated area.

The photos should be taken under controlled conditions, including the colour of the background material, distance from the camera, angle and lighting, including flash, in order to achieve consistent, high-quality before & after pictures. Each picture should be accompanied with the date, visit number, subject ID, subject initials.

Vectra 3D Photography

3D photography of the breast region will be taken in all patients during the routine preoperative work-up using a commercial 3D scanner, VECTRA XR scanner (Canfield Scientific). Patients will be asked to stand with their arms in varying positions and each scanning takes approximately 1–2 seconds. Photographs will be created in both standard format and pixelated format to highlight surface contour.

Weight

Subject weight measurements should be taken before the treatment and at each follow-up visit.

Static Measurements

Additional evaluation of changes in breast shape, including upper pole fullness, breast projection, and bottoming out will be assessed by static measurements:

- Sternal Notch to Nipple
- Nipple to IMF
- Base Width (at point of breast take off from chest wall)

INMODE
aesthetic solutions

[figure not shown]
Clinical Evaluation of Safety and Efficacy of Radio-Frequency Assisted Lipolysis (RFAL) of Breast Envelope and Nipple-Areolar Complex (NAC) Position

Protocol No:
DO607738A

Rev. Date: August, 2018

SIRB ID: 6254

- Nipple to nipple.

1. Base width (BW)
2. Nipple to inframammary fold distance (N-IMF)
3. Intermammary distance
4. Sternal notch to nipple distance (SN-N)
5. Soft tissue pinch test (PT)
6. Maximum skin stretch (MSS)

EVALUATION

Three independent plastic surgeons will evaluate photographs of the preoperative and postoperative photographs at 3-, 6- and if applicable, 12-month results.

DISCONTINUATION

Subjects enrolled in the study will be free to discontinue their participation in the study at any time. A decision to discontinue participation will not prejudice their medical care. In those instances, Investigators will attempt to obtain clinical results and side effect evaluation concerning the subject prior to his/ her withdrawal.

INMODE
aesthetic solutions

Clinical Evaluation of Safety and Efficacy of Radio-Frequency Assisted Lipolysis (RFAL) of Breast Envelope and Nipple-Areolar Complex (NAC) Position

Protocol No:
DO607738A

Rev. Date: August, 2018

SIRB ID: 6254

DATA ANALYSIS

Statistical analysis of all major body factors will be performed to determine quantitatively the treatment efficacy.

The data will be analysed by the Sponsor using basic descriptive statistics, as well as comparison tests, where applicable. Treatment-related complications will be monitored and reported; if applicable, their incidence rate will be calculated and analysed for any relationship to treatment parameters and/or skin type.

RISK/BENEFIT ANALYSIS

RISKS

The risks in this surgical procedure are derived from the physical impact of the surgical treatment on the tissue, the anesthesia used and the biopsy procedure (if applicable and patient's agreement is obtained). The possible risks include pain, excessive skin redness (erythema), damage to natural skin texture (scratching, crusting, blister, burn), bleeding, bruising, infection, scarring, skin contour irregularities and/or asymmetry and pulmonary complications. Certain people may be sensitive to the anesthesia used and therefore require longer time for recovery. Some of the risks of the anesthesia are difficult breathing, redness, itching, and/or swelling at the site of the application or injection. If any of the symptoms occur, tell the study doctor immediately. The biopsy procedure carries the risks of infection and/or scarring.

Should a risk related to the treatment become evident, the physician shall provide the appropriate treatment for this event. Nevertheless, should any sort of damage occur or if the treated areas or the patient in general feel uncomfortable following treatment, the subject should inform the study center for the attention of the study physician.

Subjects will not have to pay for treatment cost that is intended to resolve study complications.

INMODE
aesthetic solutions

Clinical Evaluation of Safety and Efficacy of Radio-Frequency Assisted Lipolysis (RFAL) of Breast Envelope and Nipple-Areolar Complex (NAC) Position

Protocol No:
DO607738A

Rev. Date: August, 2018

SIRB ID: 6254

BENEFITS

Potential benefits may include measurable nipple-areolar lift, as well as improvement in the elongated, tubular appearance in those patients with severe ptosis.

ALTERNATIVES

Besides the traditional surgery for breast tightening, other options include non-invasive skin tightening procedures using lasers, bipolar or monopolar devices as well as ultrasound.

ADVERSE EVENTS

The Physician must document on the Adverse Events form, in standard medical terminology, all adverse signs and symptoms regardless of severity or frequency that are either volunteered by subjects or observed during the course of the study. Included in the description will be the nature of the sign or symptom, the date of onset, whether the event was serious, the severity, the relationship to study treatment or device, the action taken, the date of resolution, and the outcome.

- Possible serious adverse event is any event that:
 - Results in death;
 - Is immediately life-threatening (injury or illness);
 - Results in hospitalization, or prolongs an existing hospitalization;
 - Results in permanent impairment of body structure or function, or in persistent or significant disability/incapacity;
 - Results in an injury that requires medical intervention to prevent permanent impairment of body structure or function;
 - Is a device malfunction or deterioration in the characteristics and/or performance of the device that results in death or serious deterioration in health;

I N M O D E
aesthetic solutions

Clinical Evaluation of Safety and Efficacy of Radio-Frequency Assisted Lipolysis (RFAL) of Breast Envelope and Nipple-Areolar Complex (NAC) Position

Protocol No:
DO607738A

Rev. Date: August, 2018

SIRB ID: 6254

- Is a device malfunction or deterioration in the characteristics and/or performance of the device that, if it were to occur again, could result in death or serious deterioration in health;
- Is a congenital anomaly/birth defect;
- Is a malignancy (cancer);
- Is any medically significant injury, event or experience that requires medical/surgical intervention to prevent one of the outcomes listed above;
- Results in end-organ toxicity, including hematologic, renal, cardiovascular, hepatic, gastrointestinal, and central nervous system events;
- Results in unreliable test results leading to inappropriate diagnosis or therapy.

All serious adverse events, whether or not deemed expected or device-related, must be reported to the clinical monitor immediately or within 24 hours by telephone.

Anticipated adverse events in this study include: pain, excessive skin redness (erythema), damage to natural skin texture (scratching, crusting, blister and burn), bleeding, bruising, infection, scarring, skin contour irregularities and/or asymmetry, pulmonary complications, complications following reaction to surgery and/or to anesthesia. There are also specific anticipated adverse events that may occur due to the punch biopsy procedure: complications following reaction to the anesthesia, infection and scarring. If an *unanticipated* adverse event occurs at any time during or after the use of the InModeRF system, the Physician must report it to the Sponsor. If the unanticipated adverse event, in the opinion of the Sponsor or the Physician, is likely to affect the safety of the subjects or the conduct of the study, the IRB will be notified of the effect within 10 working days after the Sponsor first receives notice of it.

	Clinical Evaluation of Safety and Efficacy of Radio-Frequency Assisted Lipolysis (RFAL) of Breast Envelope and Nipple-Areolar Complex (NAC) Position	
	Protocol No: DO607738A SIRB ID: 6254	Rev. Date: August, 2018

COST TO PARTICIPANTS

There is no cost to subject for participation.

COMPENSATION TO PARTICIPANTS

Patients will be compensated \$100.00 for study completion (Last 12M FU).

COMPENSATION FOR RESEARCH RELATED INJURY

In the event of a research-related injury, the sponsor of the study will pay for reasonable costs of medical treatment, except for the costs covered by the patient's medical insurance. The Sponsor will not provide any other form of compensation.

RECORDS AND REPORTS

Data from the pre/post-treatment evaluations, the treatment sessions, complications, if any, and all follow-up evaluations will be recorded on the CRFs prepared for this clinical study.

Should a subject drop from the study prematurely, the Physician will attempt to obtain clinical results and side effects evaluation concerning the subject prior to his/her withdrawal. All specified records and reports concerning this study will be forwarded to the Sponsor within a reasonable period of time.

The participating Physicians shall retain all study-related documentation for a period of two years following the date on which the clinical investigation is terminated or discontinued.

I N M O D E
aesthetic solutions

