- Poorly controlled endocrine disorders, such as diabetes or thyroid dysfunction.
- Any active condition in the treatment area, such as sores, psoriasis, eczema, and rash.
- History of skin disorders, keloids, abnormal wound healing, as well as very dry and fragile skin.
- Use of Isotretinoin (Accutane®) within 6 months prior to treatment.
- Significant systemic illness or occult systemic illness.
- Illness, infection or skin diseases localized in area of treatment.
- Other therapies or medication which may interfere with treatment.
- Breastfeeding, pregnant, or planning to become pregnant during the study.
- Allergy to lidocaine or other anaesthesia.

INMODE
aesthetic solutions

Clinical Evaluation of Safety and Efficacy of Radio-Frequency Assisted Lipolysis (RFAL) of Breast Envelope and Nipple-Areolar Complex (NAC) Position

Protocol No:
DO607738A

Rev. Date: August, 2018

SIRB ID: 6254

	
• Recent surgery in treatment area within the past 6 months.• Participation in a study of another device or drug within 3 months prior to enrolment or during this study.• As per the Investigator's discretion, any physical or mental condition which might make it unsafe for the patient to participate in this study.• As per the practitioner's discretion, refrain from treating any condition that might make it unsafe for the patient.
Risk to the Subject	
Risks involved with study participation, include:
 
1. Pain2. Excessive swelling (Edema)3. Excessive skin redness (Erythema)4. Bleeding5. Bruising6. Burn7. Blistering8. Crusting9. Scarring10. Skin pigmentation, textural, and/or contour alterations11. Infection12. Asymmetry13. Temporary injury to nerves (neuropraxia) where nerve branches are superficial

I N M O D E
aesthetic solutions

Clinical Evaluation of Safety and Efficacy of Radio-Frequency Assisted Lipolysis (RFAL) of Breast Envelope and Nipple-Areolar Complex (NAC) Position

Protocol No:
DO607738A

Rev. Date: August, 2018

SIRB ID: 6254

Scope and Duration of the Study

The clinical study will include up to 10 subjects at one site. Eligible subjects will receive single treatment according to the study protocol and will be followed up for a period of up to 1 year to document treatment safety and efficacy.

DEVICE DESCRIPTION

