The InModeRF is a Radio-Frequency device comprising of the following main modules:

- AC/DC power supply isolating system modules from AC voltage
- RF generator providing output of RF power to the hand piece
- Microcontroller controlling RF output, monitoring tissue electrical parameters, skin surface temperature and proper functioning of electronic modules.

InModeRF DEVICE

Hand piece delivers RF power to the subject and has the following main elements

- Internal electrode insulated with Teflon with a treatment tip at the distal end
- External electrode with temperature sensor
- Mechanism adjusting distance between electrodes

[figure not shown]
I N M O D E
aesthetic solutions

Clinical Evaluation of Safety and Efficacy of Radio-Frequency Assisted Lipolysis (RFAL) of Breast Envelope and Nipple-Areolar Complex (NAC) Position

Protocol No:
DO607738A

Rev. Date: August, 2018

SIRB ID: 6254

HAND PIECE

Principles of operation

Operation of InModeRF device is based on the concept of a minimally invasive procedure. The hand piece is comprised of two electrodes where an internal electrode is inserted into subcutaneous fat layer and its size is designed for thermal destruction of adipose tissue with RF energy. A second external electrode is applied to the skin surface. Both electrodes have a rigid connection with an adjustable distance between them. RF power and tip size of the internal electrode are designed to liquefy fat in the vicinity of the electrode tip. The external electrode has a much larger area that creates much lower power density on the skin of the patient. The RF current flows from the internal electrode to the external electrode. The hand piece can monitor both tissue impedance and temperature in real time. The outer temperature measurement acts as safety mechanism that stops the RF current in the case the skin temperature is reaches the desire temperature set by the doctor. The figure below shows RF energy distribution in tissue between electrodes.

[figure not shown]
I N M O D E
aesthetic solutions

Clinical Evaluation of Safety and Efficacy of Radio-Frequency Assisted Lipolysis (RFAL) of Breast Envelope and Nipple-Areolar Complex (NAC) Position

Protocol No:
DO607738A

Rev. Date: August, 2018

SIRB ID: 6254

RF energy distribution between electrodes

STUDY DESIGN

Prospective, self-controlled, open label, single arm clinical study

CLINICAL PROCEDURE

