APPENDIX I
STUDY SCHEMATICS

	Visit 1 Pre Tx 1	Visit 2 Tx 1	Visit 3 1 W FU	Visit 4 6 W FU	Visit 5 3 M FU	Visit 6 6 M FU	Visit 7 12 M FU
Informed consent process	X						
Eligibility & medical history	X						
Final enrollment	X						
Mammogram	X						
CRF measurements: Weight, static measurements	X	X	X	X	X	X	X
Photography	X	X	X	X	X	X	X
3D Image	X	X	X	X	X	X	X
Treatment ^[1]	X						
Removal of stitches			X				
Physician assessment of results			X	X	X	X	X
Subject satisfaction			X	X	X	X	X
End of study							X

	Clinical Evaluation of Safety and Efficacy of Radio-Frequency Assisted Lipolysis (RFAL) of Breast Envelope and Nipple-Areolar Complex (NAC) Position	
	Protocol No: DO607738A SIRB ID: 6254	Rev. Date: August, 2018

^[1] It is important to document what kind of anesthesia was used during the treatment and if tumescent fluid was used as well which may influence the subject's sensation.

References

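### The 5-point ratings by an unmasked physician and the woman are neither kept independent of each other nor ranked against the planned independent photograph review

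*Combined protocol and SAP*

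**What the plan says.** The Study Design section describes a "Prospective, self-controlled, open label, single arm clinical study". The synopsis, under Scope and Duration, adds: "The clinical study will include up to 10 subjects at one site".

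The subjective ratings appear in three places:

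- Visit 3 (1 week) carries a bracketed instruction: "Patient and physician satisfaction forms to be completed on 5-point scale at each post op visit".
- Visits 4 to 7 (6 weeks, 3 months, 6 months and, if applicable, 12 months) each state: "Patient and PI will fill in the questionnaires".
- The Appendix I schedule has a row headed "Physician assessment of results" and a subject satisfaction row. Both are marked at Visits 3-7 and at neither Visit 1 nor Visit 2.

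The Evaluation section provides separately for outside review: "Three independent plastic surgeons will evaluate photographs of the preoperative and postoperative photographs at 3-, 6- and if applicable, 12-month results".

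The Study Objectives entry of the synopsis ties efficacy to Vectra 3D imaging. Data Analysis promises descriptive summaries and unspecified comparison tests, carried out by the sponsor, and mentions neither the forms nor the surgeons' review. On the investigator's part in treatment, the Treatment Parameters Study section says: "The investigator may decide to have different parameters on the same patient".

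**The concern.** A physician who knows what was done, and who has an interest in the result, tends to score it generously. A woman's satisfaction score may also rise if she gives it in front of the clinical team. If either rater can see the other's form, agreement between the two is not independent support.

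A single-arm study has no comparison group in which such optimism would cancel, so any inflation in these scores would look like benefit. The before/after design does not help here, because the schedule marks no baseline rating for either form.

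The plan also produces two physician ratings at some visits without saying which one is the physician-rated result. That choice could then be made after both sets of scores are known.

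**Working it through.** The plan states no figure to reproduce: no success rule, responder definition, alpha, power or standard deviation. The check is mainly a comparison of sections.

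**1. Who rates, and when**

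| Rating | Rater | Time points | Source |
|---|---|---|---|
| Physician 5-point form | Physician at Visit 3; PI at Visits 4-7 | 1 and 6 weeks; 3, 6 and, if applicable, 12 months | Visits 3-7, Appendix I |
| Patient 5-point form | The woman | Same visits | Visits 3-7, Appendix I |
| Photograph evaluation | Three independent surgeons | 3, 6 and, if applicable, 12 months | Evaluation |

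The physician form is used at five visits. It overlaps with the surgeons' evaluation at three of them (Visits 5, 6 and 7), and at those three there are two physician ratings of the same woman.

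**2. Are the two forms kept independent?** The visit descriptions, Evaluation, Data Analysis and Appendix I give no order of completion, no private completion by the woman, and no rule that the PI scores without seeing her answer.

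**3. Is there a ranking?** Neither Evaluation nor Data Analysis says whether the PI's score or the surgeons' evaluation is the physician-rated result, or that the PI's score is only supportive.

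**4. Is the surgeons' evaluation masked?** The surgeons are called independent, but no masking to time point is stated. The Photography section has each picture carry its date and visit number, and no section has these removed before review. No rating scale for the surgeons and no rule for combining their three ratings is given.

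**5. How much could a few ratings matter?** The following is illustrative only; the documents contain no rating data.

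- With n = 10, one woman reclassified as favourable moves the rate by 1/10 = 10 percentage points. Starting from an assumed 50%, two or three such women give 70% to 80%.
- A one-category shift in two or three of 10 women raises the mean score by 2/10 = 0.2 to 3/10 = 0.3.
- Suppose no true effect means a favourable probability p = 0.5, and success means at least 9 of 10 favourable. The chance of success is P = 10·p⁹·(1−p) + p¹⁰. At p = 0.5 this is 11/1024 = 0.0107. If optimism alone raises p, the chance of a false success becomes:

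| p | Chance of at least 9 of 10 |
|---|---|
| 0.6 | 0.046 |
| 0.7 | 0.149 |
| 0.8 | 0.376 |
| 0.9 | 0.736 |

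The 50% start, the 9-of-10 rule and the values of p are assumptions. The table shows how sensitive a 10-woman rating is to optimism; it does not estimate the bias in this study.

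**The case against.** The strongest reply is that these forms do not carry the efficacy claim. The objective rests on Vectra 3D imaging, Data Analysis speaks of a quantitative assessment of body factors, and static breast measurements are also taken. Neither form is named as an endpoint or tied to a success rule. This stands, and it limits the point to the subjective ratings.

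A second reply is that the outside safeguard already exists: the Evaluation section names only the independent surgeons, and the Visit 3 text calls the forms satisfaction forms. This stands in part. A reader might infer from the Appendix I row label that the PI's score is given the same standing as the surgeons' evaluation. A label in a visit schedule says nothing about evidential weight, so the documents do not support that. They do not state the opposite either, and it is this silence that needs filling.

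Third, the questionnaires and case report form are not among the documents reviewed and could contain completion instructions. That is fair. A reader might infer that the woman answers in front of the investigator, or that each sees the other's score. The text shows only that nothing prevents it.

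Fourth, open-label treatment is unavoidable here, and satisfaction has to come from the woman. That also stands. The surgeons can take the place of the PI's rating of the result, but not of her self-report, and private completion does not remove her knowledge that she was treated.

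**Conclusion.** The point holds as a low-priority, low-cost improvement. At the post-operative visits an unmasked physician, named as the PI from Visit 4 on, and the woman each complete a 5-point form. The supplied text neither keeps the forms independent nor says how the PI's score ranks against the surgeons' evaluation. Upward is the expected direction of bias, but its size cannot be estimated from the documents.

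Two stronger readings should be avoided. A reader might infer that the PI is grading the PI's own procedure. That is reasonable for a one-site study in which the investigator may choose the parameters, but no section says that the PI operates the device. The point does not depend on it, since the PI is unmasked and has an interest in the result either way. A reader might also infer that the surgeons' evaluation, being independent, is already free of this problem. Without stated masking, and with dated and visit-numbered photographs, it is not shown to be.

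**What to change.** 1. In Evaluation and Data Analysis, name the three independent surgeons' evaluation at 3, 6 and, if applicable, 12 months as the physician-rated efficacy result. State its scale and how the three ratings are combined. List the PI's score separately as unmasked and supportive.
2. Before the surgeons review the photographs, replace date and visit labels with a code and randomise the before/after order. Masking may be imperfect if marks of the procedure are visible.
3. At each post-operative visit, have the woman complete her form alone before she is examined and return it sealed. The PI scores without seeing it. Report her satisfaction as an open-label self-report.

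This takes a few sentences, a change in the order of steps at the visit, and a little extra photograph handling. It needs no additional assessor, visit or subject. The downsides are that no physician-rated efficacy result is available before 3 months (the 1-week and 6-week physician scores remain as supportive data) and that the ratings may be less favourable.
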